8.8 Plans for Interim Analysis

No formal interim analyses were planned in the protocol that would have the intent of altering the study design. However, given the lower than anticipated follow-up that was initially observed in the study, reviews of data for completeness of endpoint data were performed when the initial study enrollment of 30 subjects was completed. The intent of these analyses and data reviews were to attempt to assess the overall completeness of the dataset.

8.9 Handling of Missing Data

All summaries will be performed only on enrolled subjects and only observed data will be summarized. There will be no imputation of data for early terminated subjects or for missing data within the database.

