7.0 STUDY SCHEDULE AND ASSESSMENTS

Table 1 provides a schedule of data collection and follow-up windows. It should be noted that certain data is collected while on and/or off GERD medications.

Standard of care practices for antireflux surgery will be the basis of the assessments performed to determine if a subject is a candidate for the LINX device. Investigators should refer to the LINX Instructions for Use (IFU) for prescribing information (see **Appendix A**). Further, the study center will obtain appropriate study informed consent prior to evaluating the subject study specific evaluations. Data will then be collected at the screening/baseline visit, the implant procedure and the hospitalization period following implant until discharge. The subject will be followed at 2-weeks, 3-months, 6-months, and 12-months post-implant, with data collection occurring at each time point. Follow-up assessments may be completed by telephone or visit, with the exception of the X-rays, manometry, barium swallow, endoscopy and esophageal pH testing which must be conducted during a visit.

Subjects will complete questionnaires to evaluate reflux-related symptoms (GERD-HRQL and Foregut Symptom Questionnaire). With the exception of the GERD-HRQL

at baseline, the questionnaires are completed off GERD medications for at least 7 days, with the exception of antacids which can be taken up until the morning of assessment. At the screening/baseline visit, the questionnaires will be completed twice for the GERD-HRQL – once on GERD medications and once off GERD medications for at least 7 days, with the exception of antacids which can be taken up until the morning of assessment (Table 2).

Table 1: Schedule of Data Collection and Follow-Up Windows

Screening/ Baseline	Implant /Discharge	2-week Post-Operative Visit (Day 7 – Day 21)	3 months (Day 76 – Day 104)	6 months (Day 150 – Day 210)	12-month Visit (Day 305 – Day 425)	Data Collected
X						Demographics (gender, race)
X					X	Height and Weight
X					X	Medical History
	X					Implant Procedure and Discharge Data
X					X	Endoscopy (LA Grade Classification)
X					X	Manometry/Motility
X	X ³				X	Barium Esophagram
	X ³				X	Upright, Bi-Planar X-Rays (AP and Lateral)
X			X	X	X	GERD Medications
X ¹			X ²	X ²	X ²	GERD-HRQL
X ²			X ²	X ²	X ²	Foregut Symptom Questionnaire
X ²					X ²	Esophageal pH Measurements (off PPIs)
	X	X	X	X	X	Device and/or Procedure Adverse Events

X=All study subjects

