Interval windows are not defined for the purpose of analysis in this study outside of the visit windows that are provided in the Study Schedule and Assessments in the final protocol. There will be no assigning of observations to time points outside of the visit to which they are recorded in the electronic Case Report Forms (eCRFs). Data collected in Unscheduled Visits forms will be listed as such. Observations collected outside of the 12-month protocol-specified visit window may be still be included in the analysis of primary effectiveness and safety endpoints since the device under study is an implant and longer term follow-up (i.e. beyond 12-months) is still considered informative towards evaluating the overall benefit-risk profile of the device in subjects with prior LSG surgery.

5 Levels of Significance

No formal statistical hypotheses are specified for this study. For continuous efficacy parameters, the p-value for a one sample, paired t-test to test if there is statistical evidence that the change from baseline is not equal to zero will be given. All estimation of endpoints will be performed using 95% confidence intervals.

6 Analysis Sets

All subjects who meet the eligibility criteria, provide informed consent, complete baseline assessments and undergo the LINX procedure will represent the study population for analysis. This set of subjects will be labeled as Full Analysis Set (FAS). This set of subjects will be identified by having answered “Yes” to the question “Was the LINX device implanted?” on the Implant Data eCRF.

7 Sample Size Justification

No formal sample size calculation has been performed for this study. The sample size planned for the study is up to 30 eligible subjects recruited from 12 clinical sites and no site will enroll more than 6 subjects without prior written approval provided by the Sponsor. No formal hypothesis has been tested in this study; thus, the sample size is not statistically sized, but rather is considered

sufficient for a descriptive summary of LINX performance for subjects who have had prior gastric surgery with LSG through confidence interval estimation and evaluation of safety and efficacy.

8 Analyses to be Conducted

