8.5.1 Esophageal Acid Exposure

Testing will be performed with subjects off PPIs. The subject's total distal esophageal acid exposure time at baseline will serve as the control and will be compared to results at the 12-month visit. Normalization for total distal ambulatory esophageal pH testing is defined as pH < 4 for < 4.5% of the time. If longer pH evaluations are received, the total distal acid exposure time will be recorded as a 24-hour average (e.g. 48-hour Bravo testing).

The proportion of subjects achieving pH normalization or at least a >50% reduction from baseline to the result at the 12-months will be summarized descriptively for the FAS. Two-sided 95% CI will also be constructed using exact Clopper-Pearson method.

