Median (Min, Max)	xx.x (xx, xx)	xx.x (xx, xx)

Denominator and percentages are based on subjects with non-missing data.

Table 6
 Bravo pH Normalization or $\geq 50\%$ Reduction Compared to Baseline (Off PPI)
 Full Analysis Set

Parameter	Baseline	12 Months Follow-Up	Change from Baseline to 12 Months Follow-Up	% Successful at 12 Months Follow-Up [1]
Total % Time				
n	xx	xx	xx	
Mean (SD)	xx.x (xx.x)	xx.x (xx.x)	xx.x (xx.x)	
Median (Min, Max)	xx.x (xx, xx)	xx.x (xx, xx)	xx.x (xx, xx)	
95% Confidence Interval			(xx.xxx, xx.xxx)	
p-value[2]			0.xxx	
Number of Subjects were Successful				xx (xx.x%)
Number of subjects with pH normalization ($\leq 4.5\%$)				xx (xx.x%)
Number of subjects with $\geq 50\%$ reduction in total distal acid exposure				xx (xx.x%)

Denominator and percentages are based on subjects completed baseline and 12 months follow-up.

[1] % Successful is defined as number of subjects meeting the success criterion of pH normalization or at least 50% reduction in total distal acid exposure.

[2] From one-sample, paired t test against the change from baseline is equal to zero.

Table 7
Summary of DeMeester Score Components
Full Analysis Set

Parameter	Baseline	12 Months Follow-Up	Change from Baseline to 12 Months Follow-Up
Daily Average of Total % Time			
n	xx	xx	xx
Mean (SD)	xx.x (xx.x)	xx.x (xx.x)	xx.x (xx.x)
Median (Min, Max)	xx.x (xx, xx)	xx.x (xx, xx)	xx.x (xx, xx)
Daily Average of Upright % Time			
n	xx	xx	xx
Mean (SD)	xx.x (xx.x)	xx.x (xx.x)	xx.x (xx.x)
Median (Min, Max)	xx.x (xx, xx)	xx.x (xx, xx)	xx.x (xx, xx)
Daily Average of Supine % Time			
n	xx	xx	xx
Mean (SD)	xx.x (xx.x)	xx.x (xx.x)	xx.x (xx.x)
Median (Min, Max)	xx.x (xx, xx)	xx.x (xx, xx)	xx.x (xx, xx)
Daily Average of Number of Reflux Episodes (pH <4)			
n	xx	xx	xx
Mean (SD)	xx.x (xx.x)	xx.x (xx.x)	xx.x (xx.x)
Median (Min, Max)	xx.x (xx, xx)	xx.x (xx, xx)	xx.x (xx, xx)
Daily Average of Number of Reflux Episodes > 5 mins			
n	xx	xx	xx
Mean (SD)	xx.x (xx.x)	xx.x (xx.x)	xx.x (xx.x)
Median (Min, Max)	xx.x (xx, xx)	xx.x (xx, xx)	xx.x (xx, xx)
Daily Average of Longest Reflux Episode (min)			
n	xx	xx	xx
Mean (SD)	xx.x (xx.x)	xx.x (xx.x)	xx.x (xx.x)
Median (Min, Max)	xx.x (xx, xx)	xx.x (xx, xx)	xx.x (xx, xx)

Note: For all parameters, the within subject average of the values within a visit is first calculated prior to summarizing across all subjects at the given visit.

Table 7
 Summary of DeMeester Score Components
 Full Analysis Set

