Number of Subjects with at Least 50% Reduction on GERD-HRQL				xx (xx.x%)

Denominator and percentages are based on subjects completed baseline and 12 months follow-up per protocol requirements.

[1] % Successful is defined as number of subjects meeting the success criterion of at least 50% reduction on GERD-HRQL at 12 months follow-up compared to baseline off PPI.

Table 15
 Daily PPI Medication Use from Baseline to 12 Months
 Full Analysis Set

Parameter	Baseline	12 Months Follow-Up	Change from Baseline to 12 Months Follow-Up	% Successful at 12 Months Follow-Up [1]
PPI Use (mg) [2]				
n	xx	xx	xx	
Mean (SD)	xx.x (xx.x)	xx.x (xx.x)	xx.x (xx.x)	
Median (Min, Max)	xx.x (xx, xx)	xx.x (xx, xx)	xx.x (xx, xx)	
95% Confidence Interval			(xx.xxx, xx.xxx)	
Number of Subjects with at Least 50% Reduction in Daily Use				xx (xx.x%)

Denominator and percentages are based on subjects completed baseline and 12 months follow-up.

[1] % Successful is defined as number of subjects meeting the success criterion of at least 50% reduction in daily PPI use from baseline at 12 months.

[2] PPI Use is defined by the evaluation of subject's daily dose of PPI.

<Programming note those PPI administrated as PRN will not be included in daily dose calculation..>

Table 16
 Abdominal/Chest X-Ray at 12 Months Follow-Up
 Full Analysis Set

Characteristic	12 Months Follow-Up (N = ##)
Is the LINX device at the gastroesophageal junction?	
Yes	xx.x (xx.x)
No	xx.x (xx.x)
Any Evidence of Device Migration?	
Yes	xx (xx.x%)
No	xx (xx.x%)

Denominator and percentages are based on subjects with non-missing data.

Table 17
 Foregut Symptoms Questionnaire by Visit (Off PPI)
 Full Analysis Set

Characteristic	Baseline (N = ##)	3 Months Follow-Up (N = ##)	6 Months Follow-Up (N = ##)	12 Months Follow-Up (N = ##)
Regurgitation Frequency				
None	xx (xx.x%)	xx (xx.x%)	xx (xx.x%)	xx (xx.x%)
Mild	xx (xx.x%)	xx (xx.x%)	xx (xx.x%)	xx (xx.x%)
Moderate	xx (xx.x%)	xx (xx.x%)	xx (xx.x%)	xx (xx.x%)
Severe	xx (xx.x%)	xx (xx.x%)	xx (xx.x%)	xx (xx.x%)
Lung Problems				
None	xx (xx.x%)	xx (xx.x%)	xx (xx.x%)	xx (xx.x%)
Recurrent cough	xx (xx.x%)	xx (xx.x%)	xx (xx.x%)	xx (xx.x%)
Nocturnal cough	xx (xx.x%)	xx (xx.x%)	xx (xx.x%)	xx (xx.x%)
Recurrent pneumonitis	xx (xx.x%)	xx (xx.x%)	xx (xx.x%)	xx (xx.x%)
Asthma	xx (xx.x%)	xx (xx.x%)	xx (xx.x%)	xx (xx.x%)
Change of voice	xx (xx.x%)	xx (xx.x%)	xx (xx.x%)	xx (xx.x%)
Other	xx (xx.x%)	xx (xx.x%)	xx (xx.x%)	xx (xx.x%)
Ability to Vomit				

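### The three 12-month responder rates are completer rates, and the plan does not show how far missing results could move them

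*SAP*

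**What the plan says.** **Missing-data rule.** SAP 8.9 states that "All summaries will be performed only on enrolled subjects and only observed data will be summarized", with nothing imputed for early terminations or gaps in the database. Protocol 10.4 likewise analyses available data.

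**Population and denominators.** SAP section 6 defines the FAS and identifies it by device implantation. SAP 8.5.1 says that the pH responder proportion "will be summarized descriptively for the FAS". The footnotes to Tables 6 (pH) and 15 (PPI dose) read: "Denominator and percentages are based on subjects completed baseline and 12 months follow-up". For Table 14 (GERD-HRQL) the footnote is "Denominator and percentages are based on subjects completed baseline and 12 months follow-up per protocol requirements". All three tables are headed Full Analysis Set. Adverse event percentages in Tables 20 and 21, by contrast, use every FAS subject.

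**Follow-up.** SAP 8.8 explains that completeness reviews were made "given the lower than anticipated follow-up that was initially observed in the study". It gives no rate. SAP section 4 allows 12-month observations from outside the visit window to be used.

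**Mode of collection.** Protocol 7.0: "Follow-up assessments may be completed by telephone or visit, with the exception of the X-rays, manometry, barium swallow, endoscopy and esophageal pH testing". The excepted tests need a visit.

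**Size.** SAP section 7: "No formal sample size calculation has been performed for this study", and "The sample size planned for the study is up to 30 eligible subjects recruited from 12 clinical sites".

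**The concern.** The concern is with subjects who were implanted but have no 12-month result for an endpoint. They leave the numerator and the denominator together, so the reported rate describes those who came back or could be reached.

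The group can differ by endpoint. The pH test needs a clinic visit, while GERD-HRQL and medication use may be obtained by telephone. Table 14 also limits its denominator to those meeting protocol requirements, a term the SAP does not define. If it includes the seven days off GERD medication, a subject who could not stop medication would drop out of the GERD-HRQL rate but stay in the PPI rate. The three percentages may then describe three different subsets under one FAS heading.

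The three rates are the protocol's listed 12-month efficacy measures (Protocol 5.2), and the objective is to support a labeling statement by showing outcomes similar to those behind premarket approval (Protocol 3.0). The planned confidence interval reflects sampling error among those observed. It says nothing about those who are absent.

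**Working it through.** The documents give no expected responder rate, dropout rate or sample size calculation, so there is no plan figure to reproduce. The check asks how far missing results could move a rate.

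**Inputs**
- N = 30 implanted: the planned maximum in SAP section 7. SAP 8.8 speaks of an initial enrollment of 30, so the final N may differ.
- Interval: two-sided 95% Clopper-Pearson. SAP 8.5.1 names it for pH only. SAP 8.5.3 plans an interval for PPI without naming a method, and SAP 8.5.2 plans none for the GERD-HRQL responder rate.
- Number missing m: not in the documents. Assumed range 10% to 40% of 30.
- Observed success near 80%: assumed.
- No explants among the missing: assumed. Each explanted subject held as a non-responder lowers the upper bound by 1/30 = 3.3 points.

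**Formulas**, with n = N − m observed and x responders
- Observed-case rate: x/n
- Lower bound (missing = non-response): x/N
- Upper bound (missing = response): (x + m)/N
- Width between bounds: m/N, the missing share
- Observed rate minus lower bound: x/n − x/N = (x/n)(m/N)

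**Results**

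| Missing | Observed rate | Exact 95% CI | Lower bound | Upper bound |
|---|---|---|---|---|
| 3 (10%) | 22/27 = 81.5% | 61.9–93.7% | 22/30 = 73.3% | 25/30 = 83.3% |
| 5 (16.7%) | 20/25 = 80.0% | 59.3–93.2% | 20/30 = 66.7% | 25/30 = 83.3% |
| 6 (20%) | 19/24 = 79.2% | 57.8–92.9% | 19/30 = 63.3% | 25/30 = 83.3% |
| 9 (30%) | 17/21 = 81.0% | 58.1–94.6% | 17/30 = 56.7% | 26/30 = 86.7% |
| 10 (33.3%) | 16/20 = 80.0% | 56.3–94.3% | 16/30 = 53.3% | 26/30 = 86.7% |
| 12 (40%) | 14/18 = 77.8% | 52.4–93.6% | 14/30 = 46.7% | 26/30 = 86.7% |

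With 5 missing, the lower bound is 0.80 × 5/30 = 13.3 points under the observed rate. With 10 missing it is 0.80 × 10/30 = 26.7 points under.

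Up to 20% missing, the lower bound stays inside the observed-case interval. From 30% it lies below the lower limit (56.7% against 58.1%; 53.3% against 56.3%; 46.7% against 52.4%). The crossing point depends on the assumed rate. At 30% missing, 15/21 = 71.4% has a lower limit of 47.8% and a lower bound of 50.0%, still inside. 19/21 = 90.5% has a lower limit of 69.6% and a lower bound of 63.3%, outside.

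The lower bound has its own sampling error: the exact 95% CI for 20/30 is 47.2–82.7% and for 16/30 is 34.3–71.7%.

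**The case against.** **The missing data are visible.** This stands in large part. Table 1 gives the FAS count, completions, and withdrawals with reasons. Tables 6, 14 and 15 show n at each visit and for the change. Subject-level listings are planned, and Protocol 15.3 requires missing CRF data to be explained. A reader might infer that the plan hides its losses; the documents do not support that. What is absent is a display of the effect on the rates and a per-endpoint tabulation of reasons. Table 1 gives study-level reasons only, so a subject who completed the study without a pH test is not accounted for there.

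**The follow-up evidence is limited.** This also stands. SAP 8.8 speaks of what was initially observed, and the use of out-of-window data can recover some results. The final dataset may be more complete. That reduces the missing share but does not bound what remains.

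**Off-medication testing does not set pH apart.** Correct: follow-up GERD-HRQL is also completed after seven days off GERD medication. Only the required visit distinguishes the pH test. The documents do not mention declined tests.

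**The FAS label is not contradicted.** A reader might see SAP 8.5.1 and the Table 6 footnote as conflicting. They can be read together: the FAS names the eligible population, and SAP 8.9 restricts it to observed data. The label is still easy to misread as an all-implanted rate.

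**The study is descriptive and has other efficacy output.** True: continuous changes, PPI discontinuation, regurgitation and esophagitis are also reported, and no hypothesis is tested. The issue is therefore the meaning of an estimate, not type I error. An estimate offered in support of labeling still needs a clear denominator and a view of its missing-data uncertainty.

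**Conclusion.** The point holds as a gap in display and sensitivity analysis. The three responder rates are completer rates under an FAS heading, may rest on different subsets, and come with no bound for missing results in the SAP text. Part of the table shells between Tables 21 and 29 was not available for this check, but SAP 8.9 gives no sign of a sensitivity analysis there.

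The gap between the bounds equals the missing share for any N when no missing subject was explanted. With few missing, the observed-case interval covers the lower bound. At about a third missing and 80% observed success, it does not. These sizes rest on assumed missingness and success rates.

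Two stronger readings should be resisted. One is that the reported rates will be inflated: the direction is unknown, and if the missing subjects did well the observed rate is too low. The other is that a favourable conclusion should have to survive the lower bound: the study sets no success threshold, so there is nothing to test that bound against.

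**What to change.** Keep the observed-case rates. Add to Tables 6, 14 and 15:

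1. The rate over all FAS subjects, with a missing 12-month result counted as non-response, and an exact 95% CI.
2. A best-case rate over the same denominator, with missing counted as response, except that explanted subjects stay non-responders in both bounds. Protocol 11.9 requires no further testing after explant, so without this exception the best case would count them as successes.
3. The number missing for each endpoint, with the reason.
4. The three rates in the common set of subjects with all three results.

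State in SAP 8.9 that where the bounds differ materially from the observed-case rate, the result is reported as dependent on missing data.

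The cost is SAP wording and a few table rows; no new data are needed. If the SAP is already closed, SAP 8.1 provides for identifying such departures in the output and documenting them in the study report. The downside is that the lower bound is pessimistic and the displayed result will look less favourable.

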4.0 STUDY RATIONALE

The LSG procedure involves removal of the fundus. As a result, fundoplication is extremely difficult to perform with the limited amount of fundus tissue present in patients with prior LSG. Roux-en-Y Gastric bypass (RYGB) has been recommended as a conversion procedure for those who develop or continue to have reflux after LSG. However, LINX has been considered as an alternative and less invasive option that may potentially have fewer complications compared to RYGB. Additionally, patients may not be interested in RYGB due its associated malabsorption. The LINX device is implanted in the area of the gastroesophageal junction (GEJ), which is largely undisturbed with LSG. Patients with prior gastric surgery, such as LSG, have not to date been enrolled in clinical studies for the LINX device. This study is the first to prospectively enroll and evaluate under protocol the LINX device for GERD in post-LSG patients.

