11.9 ADVERSE EVENT REPORTING

If an intraoperative decision is made to not implant the LINX device, the subject will be monitored for procedure related adverse events for a period of at least three months (90 days) or longer if needed until resolution before withdrawing the subject from the study.

If a decision is made to explant the LINX device during the study, the subject will be monitored for explant-related adverse events for a period of at least three months (90 days) or longer if needed until resolution before withdrawing the subject from the study. No other study testing and/or questionnaires would be required after the device is explanted.

For all other subjects starting at the time of implantation and proceeding throughout the duration of the follow-up period, the Investigator will closely monitor each subject for the development of device and/or procedure related adverse events. A subject presenting with new onset dysphagia, abdominal pain, nausea, or vomiting, may be assessed for device migration and/or erosion if symptoms persist and benign causes cannot be established, at the discretion of the Investigator. This may include additional, non-study visit, x-rays or endoscopic evaluation. Adverse events will continue to be monitored at each of the study follow ups until resolution and/or study completion.

For the purposes of this study, a reportable event will be defined as any untoward medical occurrence which has a strong relationship to the LINX device and/or implant procedure and another etiology is unlikely. The Investigator must decide whether each event meets the definition of a Serious Adverse Event (SAE). All device and/or procedure related serious adverse events (SAE) must be reported immediately (within 5 days of discovery) to Torax Medical. SAE reporting to the IRB is per institutional policy.

An AE is considered **serious** if it meets one or more of the following criteria:

- **Is life-threatening or results in death**
Note: The term “life-threatening” in the definition of “serious” refers to an event in which the subject was at risk of death at the time of the event; it does **not** refer to an event that hypothetically might have caused death if it were more severe.
- **Requires subject hospitalization > 24 hours**
- **Requires prolongation of an existing hospitalization**
- **Results in persistent or significant disability/incapacity**
- **Results in fetal distress, fetal death, or a congenital anomaly or birth defect**

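### An explanted subject with no 12-month data stays in the Full Analysis Set but drops by default out of the 12-month responder rates, and no all-implanted analysis counts the explant

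*SAP*

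**What the plan says.** Protocol 11.9 deals with a subject whose device is removed. On assessments it says: "No other study testing and/or questionnaires would be required after the device is explanted". Explant-related adverse events are followed for at least 90 days, longer if unresolved, and the subject is then withdrawn.

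SAP section 6 defines the FAS by a yes to the implant question on the Implant Data form, so a later explant does not remove anyone from it. SAP 8.5.1 says that the pH responder proportion "will be summarized descriptively for the FAS". SAP 8.9 summarises observed data only: "There will be no imputation of data for early terminated subjects or for missing data within the database". Protocol 10.4 likewise uses available data.

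The three responder tables carry the FAS title but a narrower denominator. Tables 6 and 15 state: "Denominator and percentages are based on subjects completed baseline and 12 months follow-up". Table 14 states: "Denominator and percentages are based on subjects completed baseline and 12 months follow-up per protocol requirements". The adverse event percentages in Tables 20 and 21, by contrast, use the whole FAS.

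On timing, SAP section 4 adds: "Observations collected outside of the 12-month protocol-specified visit window may be still be included in the analysis of primary effectiveness and safety endpoints".

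Device removals are a named safety outcome (Protocol 5.1, SAP 1.2), and a programming note just before Table 29 explains how explants are identified and dated. Nothing visible in SAP 8.5, SAP 8.9 or Tables 6, 14 and 15 links explant to responder status.

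**The concern.** The study aims to confirm that efficacy after sleeve gastrectomy is similar to the outcomes behind the device's approval, in support of a labelling statement (SAP 1.1). The three 12-month responder rates are that efficacy evidence (Protocol 5.2). A subject whose device was removed counts in the adverse event denominators but can be missing from both numerator and denominator of the efficacy rates. A reader who sees the FAS title may take the percentage as referring to everyone implanted.

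Two smaller gaps follow.

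- PPI use is not clearly testing or a questionnaire, so it may be recorded until withdrawal. The same explanted subject could then appear in Table 15 and be absent from Tables 6 and 14.
- No visible rule keeps a value recorded after explant out of the completer rows.

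Missing 12-month data are a practical matter here: SAP 8.8 reports that follow-up was at first lower than anticipated, without giving a number.

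**Working it through.** The plan has no sample size calculation, expected responder rate or explant rate, so there is no planned figure to reproduce. From the documents: up to 30 implanted (SAP 1.2), a 12-month window of Day 305 to Day 425 (Protocol Table 4), at least 90 days of monitoring after explant (Protocol 11.9), and exact Clopper-Pearson intervals for the pH proportion (SAP 8.5.1). **All explant, completer and responder counts below are assumed.**

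**1. Can an explanted subject leave before the window opens?** 305 − 90 = 215. A subject explanted before about Day 215 can finish the minimum monitoring and be withdrawn before Day 305.

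**2. No other losses.** With r responders and e explants, the completer rate is r/(30 − e) and the all-implanted rate, explants counted as non-responders, is r/30. Their ratio is 30/(30 − e).

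| e | Ratio | Example, completers | Same responders over 30 | Difference (points) |
|---|---|---|---|---|
| 1 | 1.034 | 23/29 = 79.3% | 76.7% | 2.6 |
| 2 | 1.071 | 22/28 = 78.6% | 73.3% | 5.2 |
| 3 | 1.111 | 22/27 = 81.5% | 73.3% | 8.1 |
| 5 | 1.200 | 20/25 = 80.0% | 66.7% | 13.3 |

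Over assumed observed rates of about 60% to 90%, the difference is 2.0 to 3.0 points for one explant and 5.9 to 8.9 for three.

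**3. Other losses present.** Assume 30 implanted, 20 completers, 16 responders, and e explants among the 10 non-completers. The planned row is 16/20 = 80.0% (95% CI 56.3 to 94.3). With explants as non-responders, the all-implanted rate lies between two points:

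- Lower, all other missing as non-responders: 16/30 = 53.3%.
- Upper, all other missing as responders: (16 + 10 − e)/30. This is 25/30 = 83.3% for e = 1, 24/30 = 80.0% for e = 2, 23/30 = 76.7% for e = 3 and 21/30 = 70.0% for e = 5.

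With one explant, 80.0% lies inside the bounds and the direction is open. With two it equals the upper bound. Only from three is it above every possible all-implanted value. If the other losses are unrelated to outcome, the all-implanted rate for e = 3 is 0.80 × 27/30 = 72.0%.

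**4. A value recorded after explant.** Take e = 3 and suppose one explanted subject is tested voluntarily, is recorded at the 12-month visit and meets the threshold. The planned row becomes 17/21 = 81.0%. The bounds stay at 53.3% and 76.7%, because that subject still counts as a non-responder.

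**5. The extra condition in Table 14.** Suppose 2 of the 20 did not complete the questionnaire per protocol requirements. With e = 3, there are 9 other missing.

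- If both are non-responders: planned row 16/18 = 88.9%, bounds 16/30 = 53.3% and 25/30 = 83.3%.
- If both are responders: planned row 14/18 = 77.8%, bounds 14/30 = 46.7% and 23/30 = 76.7%.

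**The case against.** The strongest reply is that this is a descriptive study without hypothesis tests, that analysis of available data was specified in Protocol 10.4, and that the footnotes disclose the denominator. Each table prints its n and Table 1 gives the FAS count, so a reader can form the lower bound unaided, apart from any post-explant responder. That stands as a defence of the completer row, which should be kept. It does not supply the upper bound, which needs the number of explanted subjects without that endpoint's measurement, and it does not align the FAS title with the denominator.

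Several stronger readings go beyond the documents.

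- *No rule covers an explanted subject.* SAP 8.9 and the footnotes do: without 12-month data the subject is excluded. What is missing is a rule that treats the explant as an outcome.
- *Off-device values will be credited to the device.* A reader might note that gastric bypass "has been recommended as a conversion procedure for those who develop or continue to have reflux after LSG" (Protocol 4.0) and infer that explanted subjects improve for that reason. The documents do not say what these subjects receive. SAP section 4 keeps observations at their recorded visit, lists unscheduled data separately, and justifies late data by the device being an implant. A post-explant value would enter only if voluntary testing were recorded as a 12-month visit.
- *Explants go unreported.* They are a safety outcome with a programmed derivation. The table shells between Table 21 and Table 29, apart from that note, were not in the text reviewed, so explant counts may already be there.
- *Table 14 hides its exclusions.* Table 13 prints the number who completed the questionnaire per protocol requirements at each visit.
- *The all-implanted rate is the one comparable with the approval data.* The documents do not say how those outcomes treated explants, so neither row can be called the better match.

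**Conclusion.** The point holds as a gap in the efficacy analysis. Following the plan as written, an explanted subject without 12-month data is left out of the responder rates in Tables 6 and 14, and possibly Table 15, while remaining in the FAS. If success means response with the device in place and there are no other losses, the completer rate is overstated by 30/(30 − e).

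The actual size is unknown because no explant count is given, and it is zero if nobody was explanted. A reader might infer that the completer rate must be too high. That does not follow once other subjects are missing: in the illustration with 10 non-completers, one explant leaves the direction open, and the threshold of three belongs to those assumed counts. Counting explant as failure is itself a choice, since the visible text does not classify reasons for removal.

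**What to change.** Keep the completer rows in Tables 6, 14 and 15, label them as completers and show n. Add to SAP 8.9, marked as added after the data-completeness reviews described in SAP 8.8:

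> *For each of the three 12-month responder endpoints, a supplementary analysis uses all implanted subjects as denominator. A subject whose explant date precedes that endpoint's own 12-month measurement, or who is explanted and has no such measurement, is a non-responder whether or not later data exist. Other missing subjects are shown as two bounds: all non-responders and all responders.*

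In the three tables:

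- Add the two bounds as point values, without confidence intervals on rows that contain assumed outcomes. In 23/30, seven of the successes are assumed, so an exact interval there would not have its nominal meaning.
- State the number of explants, and the number of explanted subjects with later data who are in the completer row.
- In Table 14, carry over from Table 13 the number not completed per protocol requirements and treat those subjects as missing in the bounds.

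The cost is one SAP paragraph, two rows in each of three tables and a few footnotes, with no new data. Explant dates come from the adverse event form or have to be derived from the withdrawal reason, as the programming note already provides. The drawbacks are longer tables and, if explants occurred, possibly a less favourable figure beside the completer rate.
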